## Analysis

- The primary endpoint is defined as the proportion of men that are confirmed to have BPH based on full urologist assessment of diagnostic test results among men with a positive result on the BPE/BPO screening tool and probable BPH diagnosis as assessed by the GP. For this proportion, the numerator is number of subjects diagnosed with BPH by a urologist; denominator is number of subjects with a positive result on the BPE/BPO screening tool and a probable BPH assessment by

the GP and a BPH assessment by the urologist. The 95% confidence interval for this proportion will be presented.

- Sufficient general practice centres (50 consecutive men per centre) in various markets will be recruited to administer the BPE/BPO screening tool to 1,500 men (using protocol defined criteria) presenting to clinic for reasons unrelated to the study. It is expected that 33% of the 1,500 presenting (or approximately 500) will have a positive result on the BPE/BPO screening tool and a probable BPH assessment by GP and thus will be assessed by a urologist.
- Due to the design of the study and types of endpoints incorporated, ‘observed cases’ will be summarized for a subset of subjects in study Parts I and II. There will be no imputations for missing data or for discontinued subjects.
- An interim analysis is not planned for this study.

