### 8.2. Sample Size Considerations

Sufficient general practice centres (approximately 50 subjects per centre) in the various markets will be recruited to administer the BPE/BPO screening tool to 1,500 men using protocol defined criteria presenting to clinic. It is expected that 33% of the 1,500 presenting (or approximately 500) will have a positive result on the BPE/BPO and/or IPSS screening tools and a probable BPH assessment by GP and thus will be assessed by a urologist.

Evaluation of 500 subjects by a urologist will allow estimation of a 95% confidence interval on the primary endpoint proportion with a maximum width of  $\pm 0.044$ . Sample size assumptions are in terms of the binominal distribution with the proportion of urologist confirmed BPH diagnosis most conservatively assigned at 0.50. Using these assumptions, the following provides an overview of other possible sample sizes along with projected 95% confidence interval maximum width.

| Number of Subjects Evaluated by Urologist | Maximum Width of a 95% Confidence Interval |
|---|--|
| 300                                       | $\pm 0.057$                                |
| 500                                       | $\pm 0.044$                                |
| 700                                       | $\pm 0.037$                                |

Sample size re-estimation is not planned.

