### **8.4.2. Primary Analyses**

The primary endpoint is defined as the proportion of men confirmed to have BPH based on full urologist diagnostic testing among men with a positive result on the BPE/BPO screening tool (score  $\geq 3$ ) and serum PSA  $\geq 2$  ng/mL. Primary endpoint summaries will be descriptively presented in terms of the calculated proportion, described below, and 95% confidence interval on the proportion. Formal hypothesis testing will not be conducted.

| Tool        | Proportion  | Numerator  | Denominator  |
|-------------|---|--|--|
| BPE/
BPO | BPH Diagnosis by Urologist based upon BPE/BPO screening tool (score $\geq 3$ ) and serum PSA $\geq 2$ ng/mL | Number of subjects diagnosed with BPH based on full urologist diagnostic testing | Number of subjects with a positive result on the BPE/BPO screening tool (score $\geq 3$ ) and serum PSA $\geq 2$ ng/mL and a BPH assessment by urologist |

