**7.1.2. Planned Primary Efficacy Statistical Analyses**

Primary Statistical Analyses			
Endpoint(s)			

 
Proportion of men that are confirmed to have BPH based on full Urologist assessment of diagnostic test results among men with a positive result on the BPE/BPO screening tool (score <math>\geq 3</math>) and serum PSA <math>\geq 2</math> ng/mL.
 
Primary endpoint summaries will be descriptively presented in terms of the calculated proportion, described below, and 95% confidence interval on the proportion. Formal hypothesis testing will not be conducted.
 
			
Tool	Proportion	Numerator	Denominator
BPE/BPO	BPH diagnosis by Urologist based upon BPE/BPO screening tool (score $\geq 3$ ) and serum PSA $\geq 2$ ng/mL.	Number of subjects diagnosed with BPH based upon a BPH assessment by Urologist.	Number of subjects with a positive result on the BPE/BPO screening tool (score $\geq 3$ ) and serum PSA $\geq 2$ ng/mL and a BPH assessment by Urologist.

 
Table 3 provides an overview of the planned summaries and primary efficacy analyses. A list of planned data displays is in Appendix 15: List of Data Displays.
 
			
Model Specification			

 
No models were used during the statistical analysis; proportions and confidence intervals were computed.
 
			
Model Checking & Diagnostics			

 
Not Applicable
 
			
Model Results Presentation			

 
Not Applicable
 
			
Sensitivity and Supportive Statistical Analyses			

 
Not Applicable
 
			

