**8.1.2. Planned Secondary Efficacy Statistical Analyses**

Primary Statistical Analyses			
Endpoint(s)			
Secondary endpoints and other measures of interest are defined in terms of proportions for each: probable BPH diagnosis by GP, BPH diagnosis by Urologist, and BPH progression risk by Urologist along with use of 1) BPE/BPO screening tool and 2) IPSS screening tool. The 95% confidence intervals (calculated using the exact (Clopper-Pearson) method) for these proportions will be presented.			
Secondary Endpoints: Proportions only in terms of the BPE/BPO tool			
Tool	Proportion	Numerator	Denominator
BPE/BPO	BPH Progression Risk by Urologist based upon BPE/BPO screening tool (score $\geq 3$ ) and serum PSA $\geq 2$ ng/mL	Number of subjects diagnosed with BPH progression risk by Urologist	Number of subjects with a positive result on the BPE/BPO screening tool (score $\geq 3$ ) and serum PSA $\geq 2$ ng/mL and a BPH progression risk assessment by Urologist
BPE/BPO	Probable BPH Diagnosis by GP based upon BPE/BPO screening tool (score $\geq 3$ )	Number of subjects diagnosed with 'probable BPH' by GP	Number of subjects with a positive result on the BPE/BPO screening tool (score $\geq 3$ ) and a BPH assessment by GP

Primary Statistical Analyses			
Secondary Endpoints: Proportions only in terms of the IPSS screening tool			
Tool	Proportion	Numerator	Denominator
IPSS	BPH Diagnosis by Urologist based upon IPSS (score $\geq 8$ ) and serum PSA $\geq 2$ ng/mL	Number of subjects diagnosed with BPH based upon BPH assessment by Urologist.	Number of subjects with a positive result on the IPSS (score $\geq 8$ ) and serum PSA $\geq 2$ ng/mL and a BPH assessment by Urologist
IPSS	BPH Progression Risk by Urologist based upon IPSS (score $\geq 8$ ) and serum PSA $\geq 2$ ng/mL	Number of subjects diagnosed with BPH progression risk by Urologist	Number of subjects with a positive result on the IPSS (score $\geq 8$ ) and serum PSA $\geq 2$ ng/mL and a BPH progression risk assessment by Urologist
IPSS	Probable BPH Diagnosis by GP based upon IPSS (score $\geq 8$ )	Number of subjects diagnosed with 'probable BPH' by GP	Number of subjects with a positive result on the IPSS (score $\geq 8$ ) and a BPH assessment by GP

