**11.10. Appendix 10: Multicenter Studies****11.10.1. Methods for Handling Centers**

- The countries participating in this trial include: Russia, Germany, Italy, France, and Spain.
- In this multicentre study, enrollment will be presented by country, and separately by country and center.

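### The ±0.044 precision holds only if men are independent and all 500 enter the primary denominator; neither document allows for within-centre correlation in the pooled interval

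*Protocol*

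**What the plan says.** Protocol 8.2 plans recruitment by general practice: "Sufficient general practice centres (approximately 50 subjects per centre"), with 1,500 men screened and about 500 reaching a urologist. It states a maximum 95% CI width of ±0.044 for 500 assessed men (±0.057 for 300, ±0.037 for 700) and gives the basis: "Sample size assumptions are in terms of the binominal distribution with the proportion of urologist confirmed BPH diagnosis most conservatively assigned at 0.50".

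The protocol describes the 500 in two ways. In 8.2 they are men who "will have a positive result on the BPE/BPO and/or IPSS screening tools and a probable BPH assessment by GP". In the synopsis (Analysis) they are men who "will have a positive result on the BPE/BPO screening tool and a probable BPH assessment by GP". The primary denominator in Protocol 8.4.2 begins "Number of subjects with a positive result on the BPE/BPO screening tool" (score ≥3) and adds PSA ≥2 ng/mL and a urologist assessment. SAP 7.1.2 has the same denominator.

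For the analysis, SAP 7.1.2 says: "Primary endpoint summaries will be descriptively presented in terms of the calculated proportion, described below, and 95% confidence interval on the proportion". It names no interval method, uses no model and marks sensitivity and supportive analyses as not applicable. A method is named only for the secondary proportions, in SAP 8.1.2: "The 95% confidence intervals (calculated using the exact (Clopper-Pearson) method) for these proportions will be presented". On centres, SAP Appendix 10 says: "In this multicentre study, enrollment will be presented by country, and separately by country and center". SAP Appendix 11 excludes covariates and strata but lists country and center as subgroups that may be used. The SAP synopsis and Table 2.15 also give the primary proportion by country and center.

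**The concern.** Men from one practice share a GP who decides on probable BPH, a local laboratory for PSA and, probably, a urologist. Under Protocol 4.1 that urologist's yes/no diagnosis is the definition of confirmed BPH, and testing beyond the required assessments follows local standard of care. Each of these could make outcomes within a centre more alike than outcomes between centres. If so, 500 men carry less information than 500 independent men, and a simple binomial interval on the pooled proportion is too narrow.

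The second issue needs no correlation at all. If the 500 include men positive on IPSS only, fewer than 500 contribute to the primary estimate.

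No hypothesis is tested, so the estimate and its interval are the whole primary result. What is at stake is how precise that result appears.

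**Working it through.** **Inputs from Protocol 8.2:** 500 assessed men, p = 0.50, 95% confidence, 1,500 screened at about 50 per centre. **Derived:** 1,500/50 = 30 centres and 500/30 = 16.7 assessed men per centre. **Assumed:** every ICC, because neither document gives one.

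**1. The plan's own figures.** Half-width = 1.96 × √(0.25/n). This gives 0.0566 for n = 300, 0.0438 for n = 500 and 0.0370 for n = 700. All three rows of the 8.2 table are reproduced, so the table corresponds to a design effect of exactly 1.

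**2. Allowing for centre.** DEFF = 1 + (16.7 − 1) × ICC; effective n = 500/DEFF; half-width = 1.96 × √(0.25 × DEFF/500). Coverage comes from beta-binomial simulation (30 near-equal centres, p = 0.5, 40,000 replicates per row). The last column is the interval proposed in the fix.

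| Assumed ICC | DEFF | Effective n | Half-width | Clopper-Pearson coverage | Centre-clustered coverage |
|---|---|---|---|---|---|
| 0 | 1.000 | 500 | ±0.044 | 95.6% | 95.2% |
| 0.01 | 1.157 | 432 | ±0.047 | 93.8% | 95.0% |
| 0.02 | 1.313 | 381 | ±0.050 | 92.1% | 95.3% |
| 0.05 | 1.783 | 280 | ±0.059 | 87.2% | 95.2% |
| 0.10 | 2.567 | 195 | ±0.070 | 78.7% | 95.1% |

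With uneven centres (2 to 31 men each), Clopper-Pearson covers 93.3, 90.9, 84.5 and 74.7% at ICC 0.01 to 0.10; the clustered interval stays at 94.6-94.9%.

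For scale, 500 men are worth 300 independent men (the plan's ±0.057 row) when DEFF = 500/300, that is at ICC = (1.667 − 1)/15.67 = 0.043.

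**3. Away from p = 0.5.** Width shrinks but the design effect does not. At p = 0.76 and ICC 0.02 the half-width is 1.96 × √(0.76 × 0.24 × 1.313/500) = ±0.043, inside ±0.044; at ICC 0.05 it is ±0.050. (The 0.76 is 0.838/(0.838 + 0.26), from the sensitivity and specificity in Protocol 4.4 at an assumed 50% prevalence.) The approximate coverage of a simple interval, 2Φ(1.96/√DEFF) − 1, does not involve p. It is 93, 91, 86 and 78% at ICC 0.01 to 0.10.

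**4. The denominator.** Protocol 4 defines probable BPH as either tool positive with PSA ≥2 ng/mL, so the PSA condition should already hold among men referred. The tool condition need not, because a man with IPSS ≥8 and BPE/BPO <3 can be among the 500 of section 8.2 but cannot enter the denominator of 8.4.2. With independent men, an assumed 360 contributors would give 1.96 × √(0.25/360) = ±0.052. At 12 men per centre and ICC 0.01 to 0.10 that becomes ±0.054 to ±0.075.

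**The case against.** The size of any loss cannot be fixed from the documents. There is no ICC, and at 0.01 the effect is slight because Clopper-Pearson is conservative to begin with. The figure of ±0.044 is offered as a maximum at p = 0.5. Sensitivity, specificity and accuracy in Protocol 4.4 imply a prevalence of (0.801 − 0.740)/(0.838 − 0.740) = 62% and a positive predictive value of about 0.84. At that value 500 men still give ±0.043 at ICC 0.05. The endpoint is descriptive, no decision rule uses the interval, and by-centre tables will show variation between centres.

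Most of this stands, and it limits the weight of the point. It does not remove it. The Protocol 4.4 figures come from a urology setting, so applying them to general practice is an assumption. A narrower interval at a higher proportion still under-covers. Tables by centre display variation but do not correct the pooled interval.

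A reader might infer that the SAP rules out an adjustment for centre. It does not: Appendix 11 excludes covariates and strata but allows center as a subgroup in summaries and statistical analyses, and a cluster-based standard error needs neither covariate nor model. The documents are silent on clustering. A reader might also take Clopper-Pearson to be the stated primary method. It is named only for the secondary proportions, so the coverage figures above are illustrative for the primary; any simple binomial interval makes the same independence assumption. Finally, using 50 as the cluster size would exaggerate the effect, because about 17 men per centre are expected to be assessed.

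**Conclusion.** The point holds in conditional form. The ±0.044 is correct arithmetic for 500 independent men who all enter the primary denominator; the plan states neither condition and secures neither. If outcomes correlate within centre, the pooled interval overstates precision: little at ICC 0.01, materially at 0.05 (effective n about 280, coverage about 87%) and more at 0.10. These sizes rest on assumed ICCs, 30 centres of similar size and p = 0.5, which is the worst case for width.

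Separately, if any of the 500 are positive on IPSS only, ±0.044 is optimistic even with independent men. The documents do not say how many that would be.

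The stronger reading, that the primary result is biased or its interval known to be wrong, is not supported: the estimate is unaffected and the true ICC may be near zero. Nor do the documents say whether one urologist serves several centres or whether the urologist's identity is recorded, so no size can be put on correlation at that level. This is a worthwhile, inexpensive improvement.

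**What to change.** **Protocol 8.2 and synopsis.** State that ±0.044 assumes independent men and that all 500 enter the primary denominator. Reconcile the two descriptions of the 500. Restate the half-width for the number expected to have BPE/BPO ≥3, PSA ≥2 ng/mL and a urologist assessment, and label any ICC range as assumed.

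**SAP 7.1.2.** Name the primary CI method and keep that interval as planned. Beside it, as a supportive result, give a 95% CI clustered on GP centre, with the observed ICC: logit(p) ± t(k−1) × SE/[p(1−p)], back-transformed, where SE is the ratio-estimator standard error with centre as cluster and k is the number of contributing centres. Pre-specify that the planned interval is relied on where the clustered one is narrower, or where the proportion is 0 or 1. The first case will be common if there is no clustering: about 47% of simulated studies at ICC 0 and 26% at 0.01 (500 men, p = 0.5). If the urologist is recorded and serves several centres, repeat with urologist as the cluster; otherwise state the limitation.

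**Cost.** Some wording and a few lines of SAS. Centre is already used in the tables, so centre clustering needs no new data. At zero ICC the clustered interval averages ±0.0453 against ±0.0447 for Clopper-Pearson with 500 men, and ±0.0533 against ±0.0528 with 360, about 1-2% wider.

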### 8.3. Data Analysis Considerations

#### 8.3.1. Analysis Populations

Subjects are not randomized or dispensed study treatment. As designed in the protocol, the number of subjects will decrease from the screening period to GP Assessment (Part I) and then again in the subsequent Urologist Assessment (Part II) either due to not qualifying for progression to the next part of the study or due to any withdrawal.

The decreases, along with planned multiple summary and analysis types, will impact and restrict the evaluable population for a given endpoint. Therefore, populations are not defined in the traditional sense. Rather, for each reported summary statistic and analyses,

the subset of subjects and/or denominators will be clearly defined in the Reporting and Analysis Plan (RAP).

- Due to the design of the study and types of endpoints incorporated, ‘observed cases’ will be summarized. For the primary analyses, there will be no imputations for missing data, no imputations for missing responses within the BPE/BPO or IPSS screening tools, and no imputations for subjects withdrawing from the study or not qualifying for a subsequent part of the study.

Any pre-planned exclusions from analysis, such as for protocol deviations, will be defined in the RAP.

### **8.3.2. Interim Analysis**

An interim analysis is not planned for this study.

### **8.3.3. Multiplicity**

All pre-planned summary statistics and hypothesis testing results will be presented. There are no established controls for interpretation of the multiple outputs.

## **8.4. Key Elements of Analysis Plan**

Data will be listed and summarized according to GSK reporting standards, where applicable. Complete details will be documented in the RAP. Any deviations from, or additions to, the original analysis plan described in the protocol will be documented in the RAP and final study report.

### **8.4.1. Population Descriptive Statistics**

Numbers of subjects participating in the study will be summarized for each study period: Screening, GP Assessment (Part I), and Urologist Assessment (Part II). Numbers of subjects who do not continue to a subsequent study period, along with reason, will be summarized.

Summary statistics for CRF collected demography, medical history, and medical evaluations collected by the GP and urologist will be summarized, as applicable, for each study period.

### **8.4.2. Primary Analyses**

The primary endpoint is defined as the proportion of men confirmed to have BPH based on full urologist diagnostic testing among men with a positive result on the BPE/BPO screening tool (score  $\geq 3$ ) and serum PSA  $\geq 2$  ng/mL. Primary endpoint summaries will be descriptively presented in terms of the calculated proportion, described below, and 95% confidence interval on the proportion. Formal hypothesis testing will not be conducted.

| Tool        | Proportion  | Numerator  | Denominator  |
|-------------|---|--|--|
| BPE/
BPO | BPH Diagnosis by Urologist based upon BPE/BPO screening tool (score $\geq 3$ ) and serum PSA $\geq 2$ ng/mL | Number of subjects diagnosed with BPH based on full urologist diagnostic testing | Number of subjects with a positive result on the BPE/BPO screening tool (score $\geq 3$ ) and serum PSA $\geq 2$ ng/mL and a BPH assessment by urologist |

### 8.4.3. Secondary Analyses

Secondary endpoints and other measures of interest are defined in terms of proportions for each: probable BPH diagnosis by GP, BPH diagnosis by urologist, and BPH progression risk by urologist along with use of 1) BPE/BPO screening tool and 2) IPSS screening tool. These proportions will be calculated in terms of the numerators and denominators shown below; the 95% confidence intervals for these proportions will be presented.

| Secondary Endpoints: Proportions only in terms of the BPE/BPO tool |  |   |   |
|--|--|---|---|
| Tool   | Proportion   | Numerator   | Denominator   |
| BPE/
BPO  | BPH Progression Risk by Urologist based upon BPE/BPO screening tool (score $\geq 3$ ) and serum PSA $\geq 2$ ng/mL | Number of subjects diagnosed with BPH progression risk by urologist | Number of subjects with a positive result on the BPE/BPO screening tool (score $\geq 3$ ) and serum PSA $\geq 2$ ng/mL and a BPH progression risk assessment by urologist |
| BPE/
BPO  | Probable BPH Diagnosis by GP based upon BPE/BPO screening tool (score $\geq 3$ )                                   | Number of subjects diagnosed with 'probable BPH' by GP              | Number of subjects with a positive result on the BPE/BPO screening tool (score $\geq 3$ ) and a BPH assessment by GP  |

| Secondary Endpoints: Proportions only in terms of the IPSS screening tool |  |  |   |
|---|--|--|---|
| Tool  | Proportion   | Numerator  | Denominator   |
| IPSS  | BPH Diagnosis by urologist based upon IPSS (score $\geq 8$ ) and serum PSA $\geq 2$ ng/mL        | Number of subjects diagnosed with BPH based on full urologist diagnostic testing | Number of subjects with a positive result on the IPSS (score $\geq 8$ ) and serum PSA $\geq 2$ ng/mL and a BPH assessment by urologist                  |
| IPSS  | BPH Progression Risk by urologist based upon IPSS (score $\geq 8$ ) and serum PSA $\geq 2$ ng/mL | Number of subjects diagnosed with BPH progression risk by urologist              | Number of subjects with a positive result on the IPSS (score $\geq 8$ ) and serum PSA $\geq 2$ ng/mL and a BPH progression risk assessment by urologist |
| IPSS  | Probable BPH Diagnosis by GP based upon IPSS (score $\geq 8$ )                                   | Number of subjects diagnosed with 'probable BPH' by GP                           | Number of subjects with a positive result on the IPSS (score $\geq 8$ ) and a BPH assessment by GP  |

Additional summaries, proportions and related 95% confidence intervals, will be generated as outlined above, but in terms of a positive result for both the BPE/BPO and the IPSS screening tools.

Another secondary endpoint of this study is to assess the level of agreement between the BPE/BPO and/or IPSS screening tools for selecting men to investigate for BPH. The number and proportion of subjects with a positive or with a negative response to both the BPE/BPO and IPSS screening tools at screening will be summarized.

Agreement of the BPE/BPO and the IPSS screening tools will be assessed using the kappa coefficient. The simple kappa coefficient along with the 95% confidence interval will be generated using SAS along with hypothesis testing. The associated null hypothesis is that the two measures (BPE/BPO and IPSS screening tools) are independent, i.e.,  $\kappa = 0$ . The alternative hypothesis is that the agreement of the two measures is better than one would expect by chance. Two-sided tests of the null hypothesis will be conducted at the 0.05 level of significance.

The above defined kappa coefficient will be characterized as proposed by Landis and Koch (Landis, 1977) with  $<0$  indicating no agreement, 0-0.20 as slight, 0.21-0.40 as fair, 0.41-0.60 as moderate, 0.61-0.80 as substantial, and 0.81 – 1 as almost perfect agreement.

The proportion of men refusing further GP investigation among subjects with a positive BPE/BPO screening tool will be summarized. The proportion of subjects refusing referral to an urologist among subjects with a positive BPE/BPO screening tool and probable GP BPH diagnosis will be summarized.

The above described proportions, for both primary and secondary endpoints, will also be summarized by country.

